### 3.1.4 Response Rate (RR)

Response Rate is defined as the number (%) of patients with a best response (according to investigator assessment as recorded in the tumour evaluation CRF) of ‘responding’, regardless of the method of evaluation, and will be based on a subset of the FAS consisting of patients with at least one documented response assessment. Data obtained up until progression, or last evaluable assessment in the absence of progression, will be included in the assessment of response rate. Patients who discontinue treatment without progression, receive a subsequent anti-cancer therapy and then respond will not be included as responders in the RR.

In addition, a sensitivity analysis of RR will be performed including patients who died prior to any response assessment and classifying them as non-responders.

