## **9.2 Description of outcome variables in relation to objectives and hypotheses**

Analysis will be conducted to evaluate the following as available in the CRF:

- Baseline characteristics: demographics, relevant medical history, disease characteristics, cancer treatment history.
- Exposure to AZD9291
- Response Rate (RR):  
RR is defined as the percentage of patients with a best response of ‘responding’ by investigator assessment as recorded in the CRF.
- Overall Survival (OS):  
Overall survival is defined as the time from the date of first dose of AZD9291 in this study until death due to any cause. Any subject not known to have died at the time of analysis will be censored based on the last recorded date on which the subject was known to be alive.
- Progression Free Survival (PFS)  
PFS is defined as the time from first dose of AZD9291 in this study until the date of disease progression as recorded in CRF or death (by any cause in the absence of progression) regardless of whether the subject withdraws from therapy or receives another anti-cancer therapy prior to progression. Subjects who have not progressed or died at the time of analysis will be censored at the time of the latest date of assessment.
- Time to treatment discontinuation (TTD):  
TTD is defined as the time from the date of first dose of AZD9291 in this study until the date of AZD9291 discontinuation for any reason including disease progression, treatment toxicity, death or other reason as recorded in CRF. Subjects who are still on treatment at the time of analysis will be censored at the date of last dose received.
- Adverse events  
Serious Adverse Events [SAEs], adverse events leading to dose modification, and adverse events of special interest

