## **9.4 Methods for statistical analyses**

All analyses will be performed on the FAS population. No statistical tests will be performed, the statistical analyses will be descriptive.

Efficacy analyses will be repeated by cohorts defined by number and type of previous treatment lines and by other pre-defined subgroups of interest as pre-specified in the SAP.

Data will be summarized using descriptive statistics as appropriate. Continuous variables will be summarised by the number of observations (n), mean, standard deviation (SD), median, quartiles (Q1 and Q3), minimum, and maximum. Categorical variables will be summarised by frequency counts and percentages for each category.

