#### **9.4.2 Evaluation of secondary efficacy objectives**

PFS and TTD will be summarized similarly to OS using KM estimates of the median times to progression or death or treatment discontinuation, and quartiles together with their 95% CIs. KM estimates of the PFS or TTD rate at appropriate time points (to be defined in SAP) will be presented as well. A plot of the KM PFS and TTD curve will be produced.

The response rate will be summarised together with the 95% CI.

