## 4 ANALYSIS METHODS

### 4.1 General principles

The below mentioned general principles will be followed throughout the study:

- Descriptive statistics will be used for all variables, as appropriate. Continuous variables will be summarised by the number of observations (n), mean, standard deviation, median, minimum, and maximum. Categorical variables will be summarised by frequency counts and percentages for each category.
- For continuous data the mean and median will be rounded to 1 additional decimal place compared to the original data. The standard deviation will be rounded to 2

additional decimal places compared to the original data. Minimum and maximum will be displayed with the same accuracy as the original data.

- For categorical data, percentages will be rounded to 1 decimal place.
- SAS® version 9.3 or higher will be used for all analyses.
- As the only population considered will be the FAS, all tables, listings and figures (demographics, efficacy, safety, etc.) will be provided using this population, unless indicated otherwise.
- For time interval analyses in months, duration in months will be calculated as total duration in days/30.4375

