#### 4.1.1 Handling missing data

In general, other than for partial dates, missing data will not be imputed and will be treated as missing.

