**Response Rate**

Response rate, as defined in Section 3.1.4, will be summarised together with exact 95% confidence interval using the Clopper-Pearson method, based on a subset of the FAS consisting of patients with at least one documented response assessment. The Best Overall Response (responding, stable disease, progressing, not evaluated) will also be summarised. A sensitivity analysis of response rate will also be performed including patients who died prior to any documented response assessment and classifying them as non-responders.

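### The SAP computes the response rate and its confidence interval only on assessed patients, although the protocol puts all analyses on the FAS; the change is not declared, and no FAS rate with an interval is planned

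*SAP*

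**What the plan says.** **Protocol.** Section 9.4 states: "All analyses will be performed on the FAS population". Section 9.3 defines the FAS as all subjects with at least one dose. Section 9.2 gives the endpoint without restricting it to assessed patients ("RR is defined as the percentage of patients with a best response of" responding, by investigator assessment). Section 9.4.2 adds: "The response rate will be summarised together with the 95% CI".

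**SAP.** Under 3.1.4 the RR "will be based on a subset of the FAS consisting of patients with at least one documented response assessment". Section 4.2.7 repeats this and attaches the Clopper-Pearson 95% interval to that subset. A sensitivity analysis adds patients who died before any assessment, as non-responders; no interval is named for it. Section 4.2.7 also says: "The Best Overall Response (responding, stable disease, progressing, not evaluated) will also be summarised", with no interval and no stated denominator. RR is then repeated in every row of the subgroup table, with no separate denominator, so the 3.1.4 definition carries over. Section 6, which lists changes from protocol, is marked not applicable in both the SAP and its addendum.

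**The concern.** RR is a named secondary efficacy outcome (Protocol section 2). The population that the protocol assigns to it has been narrowed to patients with an assessment, and the place where such a change should be declared is empty. The SAP states the subset openly where it defines RR; what is missing is the declaration, and an RR with an interval on the protocol's population.

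The exclusion works in one direction. Dosed patients who withdraw, are lost, stop early or reach country closure before any assessment are left out of the main RR, and the sensitivity analysis does not bring them back. None of them can appear in the numerator, so leaving them out can only raise the rate relative to responders/FAS. SAP 3.1.2 provides for such patients in PFS by censoring those with no post-baseline assessment at Day 1, so the plan allows for them, though that rule does not say how many there are.

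**Working it through.** The documents give no expected RR, no planned RR precision and no expected unassessed share, so there is no planned figure to reproduce. What follows is algebra and illustration.

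**Inputs**
- N = 3500: expected total recruitment (Protocol synopsis).
- Assessed RR = 65%: illustrative, within the 50% to 70% that Protocol 1.4.2 cites for T790M-positive patients.
- u, the unassessed share of the FAS: not in the documents; 1%, 2% and 5% are assumptions.
- s, the share of unassessed patients who died before assessment: not in the documents; 25%, 50% and 75% are assumptions.

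**Formulas**
- Responders/FAS = RR_assessed × (1 − u)
- Gap = RR_assessed × u
- Planned sensitivity RR = RR_assessed × (1 − u) / (1 − u + u × s)

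**Overall result, Clopper-Pearson 95% intervals**

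| u | Assessed only | Responders/FAS | Gap (points) |
|---|---|---|---|
| 1% | 2252/3465 = 65.0% (63.4–66.6) | 2252/3500 = 64.3% (62.7–65.9) | 0.65 |
| 2% | 2230/3430 = 65.0% (63.4–66.6) | 2230/3500 = 63.7% (62.1–65.3) | 1.3 |
| 5% | 2161/3325 = 65.0% (63.3–66.6) | 2161/3500 = 61.7% (60.1–63.4) | 3.25 |

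The half-width is 1.60 to 1.64 points. At u = 5% the FAS estimate (61.7%) lies below the lower limit of the planned interval (63.3%).

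**Break-even u** (gap equal to the half-width of the assessed-only interval, with n = N(1 − u))
- N = 3500: 3.4% if RR is 50%, 2.5% if 65%, 2.2% if 70%. At 65%, 0.0248 × 3500 = about 87 patients.
- At RR 65%: about 6% for N = 600, 13% for N = 150 and 25% for N = 50.

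The gap therefore matters mainly overall and in large subgroups; in small ones it is lost in the width of the interval.

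**What the planned sensitivity analysis leaves** (RR 65%, N = 3500)

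| u | s = 25% | s = 50% | s = 75% | Responders/FAS |
|---|---|---|---|---|
| 2% | 64.7% | 64.4% | 64.0% | 63.7% |
| 5% | 64.1% | 63.3% | 62.5% | 61.7% |

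The excess over responders/FAS is about 1.0, 0.6 and 0.3 points at u = 2%, and 2.4, 1.6 and 0.8 points at u = 5%. The sensitivity analysis reaches the FAS rate only if every unassessed patient died.

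**The case against.** The strongest reply is that the conflict is soft and the number affected may be small.

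- **Wording.** Protocol 9.2 opens with "Analysis will be conducted to evaluate the following as available in the CRF", and SAP 4.1.1 says that, partial dates aside, "missing data will not be imputed and will be treated as missing". A patient with no assessment has no recorded best response, and neither document says in words how such a patient counts. This stands: the assessed-only rate is defensible as a supportive rate. It does not override the protocol's statement that all analyses use the FAS, and it does not explain an empty section 6.
- **Best Overall Response table.** SAP 4.1 makes the FAS the default ("all tables, listings and figures (demographics, efficacy, safety, etc.) will be provided using this population, unless indicated otherwise"), and the table has a category for patients not evaluated. The responders/FAS percentage is therefore probably visible overall, and a reader could compute an interval from the counts. This also stands, but the table's denominator is not labelled and no interval is planned.
- **u may be small.** Protocol 4.1 and Table 4 collect efficacy at each treatment visit and at discontinuation. Protocol 4.3.1 continues assessments after a stop for reasons other than progression, and SAP 3.1 accepts any method, including clinical examination. This stands and limits the size, not the direction.
- **The FAS rate has its own bias.** It counts administratively unassessed patients as non-responders. A country closes at most 90 days after reimbursement, tumour evaluation is recommended about every 12 weeks (84 days), and no data are collected after closure. A patient enrolled late could leave with no assessment. This is a reason to report both rates, not the assessed-only rate alone.
- **Redaction.** Much of SAP section 5, on interim analyses, is blacked out. The point covers the readable text only.

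**Conclusion.** The point holds. The RR population differs from the one in Protocol 9.4, SAP section 6 does not record it, and the readable plan has no RR with an interval on the FAS, overall or by subgroup. The direction relative to responders/FAS follows from the definitions and needs no assumption. The size depends on u, which is unknown: under the illustration it passes the half-width of the overall interval only above about 2.5% unassessed, and below that it may be negligible. The weight is low to moderate, because RR is secondary, descriptive and untested, and neither the sample size nor the primary OS result depends on it. It should still be corrected, because the remedy is cheap and the exclusion favours a higher reported rate.

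**What to change.** 1. Add RR = responders/FAS with its Clopper-Pearson 95% interval, overall and in the RR subgroups, beside the assessed-only RR. Extending the planned sensitivity analysis to all unassessed FAS patients would achieve the same.
2. Record the assessed-only denominator in SAP section 6 as a change from Protocol 9.4.
3. Label the Best Overall Response table as FAS.
4. Tabulate unassessed patients by reason: death, stop for toxicity, withdrawal or loss, and country closure or move to commercial supply.

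The cost is SAP wording, one more denominator carried through the existing RR tables (18 subgroup rows, including country), and one small table. No new data are needed: SAP 4.2.1 already summarises reasons for discontinuation and withdrawal and the number moved to commercial drug. The price is a second, lower rate (by assessed RR × u) in which administrative non-assessment counts as non-response. Subgroups with different closure timing could differ on it for that reason, just as subgroups with different u can differ on the assessed-only rate. The by-reason table lets the reader tell these apart.

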## 3.2 Safety

Specified safety endpoints (Serious Adverse Events (SAEs), Adverse Events (AEs) leading to dose modification, AEs of special interest (AESIs), Hy’s Law and deaths) are required to be included in the study database.

Other safety data, i.e. laboratory results (hematology, clinical chemistry and urinalysis), ECGs, and ophthalmologic assessments, are collected if performed as part of standard medical care but are not mandated in the protocol.

### 3.2.1 SAEs

SAEs will be collected throughout the study, from the date of first dose of AZD9291 until 30 days after the last dose of study medication or until disease progression, whichever is the latest. The latest version of the Medical Dictionary for Regulatory Activities (MedDRA) will be used to code the SAEs. SAEs will be graded according to the National Cancer Institute Common Terminology Criteria for AEs (CTCAE Version 4.03).

### 3.2.2 AEsIs

The following AEsIs will be collected and summarised:

- Interstitial lung disease/pneumonitis-like events,
- QTc prolongation events.

### 3.2.3 Hy's Law

Patients with potential Hy's Law criteria will be collected and summarised.

### 3.2.4 Duration of exposure

Total Exposure to AZD9291 will be defined as the time (months) from the first dose to the last dose:

- Total exposure = (last dose date where dose > 0 mg – first dose date where dose > 0 mg + 1)/30.4375

Actual exposure to AZD9291 will be the time (months) from first dose to last dose, taking into account the number of days where no dose was taken.

- Actual exposure = (last dose date where dose > 0 mg – first dose date where dose > 0 mg + 1 – total duration of dose interruption [i.e. number of days with dose = 0 mg]) /30.4375

Note: the actual exposure calculation makes no adjustment for any dose reductions that may have occurred.

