## 6.6 Management of toxicities related to AZD9291

If a patient experiences a CTCAE grade 3 or higher and/or unacceptable toxicity (any grade), where the investigator considers the event of concern to be specifically associated with AZD9291 (and not attributable to the disease or disease-related processes for which patient is being treated), dosing will be interrupted and supportive therapy administered as required in accordance with local practice/guidelines.

If the toxicity resolves or reverts to CTCAE grade  $\leq 2$  within 3 weeks of onset, treatment with AZD9291 may be restarted at the same dose (80 mg, daily) or a lower dose (40 mg, daily) using the rules below for dose modifications (Table 5) as per the investigator's evaluation and/or in discussion and agreement with the study Medical Monitor as needed. There will be no individual modifications to dosing schedule in response to toxicity, only potential dose reduction or dose interruption. Once a dose reduction is implemented, the dose of AZD9291 cannot be reverted back to 80 mg.

If the toxicity does not resolve to CTCAE grade  $\leq 2$  after 3 weeks, then the patient must be withdrawn from the study treatment and kept in observation until resolution of the toxicity.

**Table 5** Dose Interventions

Intervention	AZD9291 Dose
Starting Dose	80 mg daily
Reduced Dose	40 mg daily

If an event subsequently requires dose interruption, AZD9291 may restart at the same dose or the reduced dose, on resolution/improvement of the event at the discretion of the investigator.

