### 6.6.1 Pulmonary Symptoms

If new or worsening pulmonary symptoms (e.g., dyspnea) or radiological abnormality suggestive of interstitial lung disease are observed, the administration of AZD9291 needs to be interrupted and the study Medical Monitor must be informed. It is strongly recommended to perform a full diagnostic workup, to exclude alternative causes such as lymphangitic carcinomatosis, infection, allergy, cardiogenic edema, or pulmonary hemorrhage. The results of the full diagnostic workup (including high-resolution computed tomography, blood and sputum culture, haematological parameters) will be recorded in the CRF by the investigator. Where ILD is suspected, local practice must be followed in discussion with the study Medical

Monitor. In the absence of a confirmed diagnosis of ILD, AZD9291 may be restarted following consultation with the study Medical Monitor. In case of a confirmed diagnosis of ILD, AZD9291 must be permanently discontinued. (refer to “Guidance for the Management of AE in studies using 80mg AZD9291”)

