### 3.2.5 Treatment Compliance

Treatment compliance is defined as the number of administered doses of AZD9291 (80 mg and 40 mg pooled) taken as a proportion of the scheduled expected number of doses.

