##### **Compliance**

Treatment compliance is calculated as the proportion in percentage of the scheduled expected number of doses, i.e. (Actual exposure/Total exposure)\*100.

Compliance will be summarised as a continuous variable for the FAS.

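### Actual exposure (SAP 3.2.4) deducts zero-dose days without limiting them to the first-to-last-dose window, so a recorded interruption that ends in permanent discontinuation understates exposure and compliance and can make both negative

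*SAP*

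**What the plan says.** SAP 3.2.4 gives total and actual exposure the same window, "last dose date where dose > 0 mg – first dose date where dose > 0 mg + 1", converted to months by dividing by 30.4375. Actual exposure then takes off a further term, "total duration of dose interruption [i.e. number of days with dose = 0 mg". The sentence introducing actual exposure begins "Actual exposure to AZD9291 will be the time (months) from first dose to last dose, taking into account the number of days where no dose".

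SAP 3.2.5 opens: "Treatment compliance is defined as the number of administered doses of AZD9291 (80 mg and 40 mg pooled) taken as a proportion of the scheduled"; the denominator is the expected number of doses. SAP 4.2.6 makes this operational: "Treatment compliance is calculated as the proportion in percentage of the scheduled expected number of doses", computed as "Actual exposure/Total exposure" times 100. The same section summarises total and actual exposure for the FAS and for discontinued patients, as a continuous variable and by class. Compliance is summarised for the FAS. The SAP addendum leaves these formulas unchanged.

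The protocol describes three routes by which an interruption can become permanent:

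- Section 6.6: dosing is interrupted for toxicity; if it has not resolved to grade 2 or below after 3 weeks, "then the patient must be withdrawn from the study treatment and kept in observation until resolution of the toxicity".
- Section 6.6.1: dosing is interrupted during the pulmonary work-up. "In case of a confirmed diagnosis of ILD, AZD9291 must be permanently discontinued". No maximum length of interruption is given.
- Section 6.6.2: dosing is interrupted for QTcF prolongation and stopped permanently if this is unresolved after 3 weeks.

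Protocol 8.1 requires dose interruptions to be recorded in the CRF and makes no exception for one that is never followed by a restart.

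**The concern.** The window and the deduction are bounded differently. A zero-dose day after the last real dose lies outside the window, so it adds nothing to total exposure, yet the deduction as printed still counts it. It is excluded once by the window and then subtracted again.

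This is a separate question from whether an interruption between two dosing periods should lower compliance. Those days are inside the window, and the formula handles them as intended.

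The error runs in one direction and falls on patients whose treatment ended in an interruption. They also appear in the separate exposure summary for discontinued patients. SAP 4.1 reports minimum values, so a single early stopper could put a negative exposure or a negative compliance in a table.

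**Working it through.** The documents state no numerical result for exposure or compliance, so there is no figure of the plan's own to reproduce. The check applies the printed formulas to example records.

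**Notation**

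- W: days from first to last non-zero dose, inclusive (SAP 3.2.4). With first dose on Day 1, W is the day number of the last dose.
- I: zero-dose days inside that window.
- T: zero-dose days after the last non-zero dose.

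**Formulas**

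- Total exposure = W / 30.4375.
- Actual exposure as printed = (W - I - T) / 30.4375.
- Actual exposure with the deduction limited to the window = (W - I) / 30.4375.
- Compliance = 100 × actual / total.

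T = 21 is an illustration taken from the 3-week limits in Protocol 6.6 and 6.6.2; it is not trial data.

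| W | I | T | As printed: days; months; compliance | Limited to window: days; months; compliance |
|---|---|---|---|---|
| 100 | 14 | 0 | 86; 2.825; 86.0% | 86; 2.825; 86.0% |
| 14 | 0 | 21 | -7; -0.230; -50.0% | 14; 0.460; 100% |
| 30 | 0 | 21 | 9; 0.296; 30.0% | 30; 0.986; 100% |
| 60 | 14 | 21 | 25; 0.821; 41.7% | 46; 1.511; 76.7% |
| 90 | 0 | 21 | 69; 2.267; 76.7% | 90; 2.957; 100% |
| 100 | 0 | 21 | 79; 2.595; 79.0% | 100; 3.285; 100% |
| 365 | 0 | 21 | 344; 11.302; 94.2% | 365; 11.992; 100% |

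**Reading the table**

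1. The first row is a control: the interruption is followed by a restart, so T = 0. The two versions agree, and the printed formula works in that case.
2. For any T above 0, actual exposure is too low by T / 30.4375 months: 0.230, 0.460 and 0.690 months for T = 7, 14 and 21. Compliance is too low by 100 × T / W points, so the relative effect is largest for early stoppers.
3. Values are negative whenever I + T exceeds W. With I = 0 and T = 21, that means a last dose on Day 20 or earlier.
4. Three months is 3 × 30.4375 = 91.3 days. The Day 100 record therefore moves from the 3-to-6-month class to the under-3-month class. The Day 90 record stays in the under-3-month class either way.
5. The limited version is always above 0 and never exceeds total exposure, because the first and last days of the window are dosed days.

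**The case against.** The best defence is that the intended meaning is clear. The sentence introducing actual exposure speaks of time from first to last dose, and SAP 3.2.5 defines compliance as doses taken over doses expected, which cannot fall below zero. Read together, these point to in-window days only. That stands as a reading of intent. But the bracketed gloss states what is to be subtracted, and it has no bound. Programmed as printed, it contradicts SAP 3.2.5.

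The second defence is that the error may never arise. Protocol Table 4 and Section 5 list interruption and discontinuation separately, and SAP 3.1.3 refers to a CRF page for discontinuation of study drug. If a pause that never restarts is entered only as a discontinuation dated from the last dose, T = 0 and both versions agree. This stands: the CRF layout is not in the documents, and Protocol 8.1 does not say how an interruption that becomes permanent is coded.

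A reader might infer more than the documents support, in three ways:

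- *That the authors expected a zero-dose record to come last*, because the last dose date is qualified as non-zero. The same qualifier is on the first dose date, where no earlier zero-dose record would be expected, so it proves nothing about terminal records.
- *That interrupting and then withdrawing is the usual way patients stop for toxicity.* Protocol 6.6 to 6.6.2 permit that path, but no document gives its share. Section 4.3 also lists reasons for stopping that need no prior pause.
- *That FAS mean compliance shifts by a definite amount.* That would need the share of patients affected and the distribution of their last-dose days, and the documents give neither. The mean is also very sensitive to assumed very early stops, where compliance becomes extremely negative.

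**Conclusion.** The defect holds, conditionally. SAP 3.2.4 as printed deducts days that lie outside its own window. Where a terminal interruption is stored as zero-dose days, actual exposure and compliance are understated for that patient, and both are negative when zero-dose days exceed the window. For an individual record the size is certain once T is known: 0.69 months for a 21-day terminal interruption, or 21 compliance points if the last dose was on Day 100.

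The conclusion rests on one assumption that the documents cannot settle, namely how the CRF stores a pause that never restarts. The 21-day length is the limit named in two of the three routes; the pulmonary route has none. The number of affected patients cannot be derived.

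The reach is limited. All analyses are descriptive. Total exposure, OS, PFS, TTD and response rate do not use the deduction. What is at risk is the summaries of actual exposure (continuous and by class) and of compliance. The correction is worth making because the printed rule can give impossible values and the remedy costs almost nothing.

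**What to change.** In SAP 3.2.4, replace the bracketed gloss on the deduction with wording such as: *zero-dose days (dose = 0 mg) falling between the first and last dates with dose > 0 mg; zero-dose days after the last non-zero dose are not subtracted*. Compliance in SAP 4.2.6 then inherits the corrected value and needs no edit of its own.

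The cost is one clause in the SAP or its addendum and one condition in the program. No new data are needed and no clinical rule changes. If the CRF holds no terminal zero-dose days, no result changes either.
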